4.0 Study Endpoints (if applicable)

The primary endpoints are changes in responses on various clinical measures pre- and post-intervention: the Social Responsiveness Scale, the Social Skills Improvement System, the Quality of Play Questionnaire, the Aberrant Behavior Checklist, and the Test of Adolescent Social Skills Knowledge-Revised. We predict that participants receiving active tDCS will show greater improvement in these measures compared to those receiving sham tDCS. This will be assessed using non-parametric t-tests (IBM SPSS Statistics, Chicago, IL) conducted separately for each measure.

Secondary endpoints will be fMRI response and reaction time pre- and post-intervention on a laboratory test of attention and social information processing.

The primary safety endpoint will be self-reported adverse effects of tDCS collected after each treatment session.

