10.0 Study Design / Methods

We will conduct brain stimulation with 17 randomized adolescent participants at initial enrollment. Drop-outs are expected, with the goal of having 10 youths with ASD complete the study, with the same number of parents actively participating by the end of the experiment.

The following table summarizes the schedule of activities for a subject:

Schedule of events	Activities	Time commitment for volunteer	Compensation
Initial visit with research coordinator, Drs. [name] and [name]	Consent (parent and child)	15 min	\$25 (child) \$15 (parent)
	Medical & MRI screening (parent and child)	5 min	
	ADOS-2 & KBIT-2 (with child), clinical measures (with parent)	90 min	

	Mock scanner training with child	10-15 min	
	fMRI scanning with child	30 min	
	tDCS acclimation with child	10 min	
PEERS weekly sessions	PEERS training plus active / sham tDCS	1 hr / week x 14 weeks	\$15 per session (child) \$0 (parent)
Post-intervention visit	clinical measures (with parent), fMRI scanning (with child)	45 minutes	\$25 (child) \$25 (parent)
14-week follow-up visit	clinical measures completed online (by parent)	30 minutes	\$10 (child) \$50 (parent)

Parents will make initial phone or email contact with the study coordinator. The study coordinator will conduct a brief telephone screening to determine preliminary eligibility for the study. If eligible, the study coordinator will schedule the initial visit.

The initial visit will last approximately 3 hours. Following informed consent (see Section 9.0), an in-depth MRI screening form will be filled out by the parent and the medical history information obtained during the initial telephone interview will be reconfirmed. Any female participants will complete a pregnancy test. [name] will then conduct the ADOS and K-BIT with the child while the parent completes the following clinical outcome measures on a computer (using RedCap) in a separate room: Social Responsiveness Scale-2 [26], the Social Skills Improvement System, the Quality of Play Questionnaire, the Aberrant Behavior Checklist, and the Test of Adolescent Social Skills Knowledge-Revised [27]. The child and parent are given a 10-minute break and a healthy snack, if desired.

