A brief questionnaire about adverse effects will be completed with participants and their parents immediately following the second and last treatment sessions. Tolerance for tDCS will be monitored during tDCS delivery by noting the frequency with which a subject reported irritation, discomfort, burning or pain, whether a subject attempted to remove the tDCS leads, whether a subject wished to discontinue the procedures due to the tDCS (rather than the PEERS training). After the second and last PEERS sessions, the experimenters will administer a brief questionnaire with the subject about whether they felt uncomfortable itching, tingling, burning during the session or whether they have had headaches, neck pain, sleepiness, moodiness in the past week. Any of these effects will be recorded. We will conclude that tDCS can be tolerated if these effects are experienced less than 25% of the time for a given individual. We will also report on how many subjects tolerated the procedures.

The child and parent receive compensation in the form of gift cards following each visit to MUSC (see Table above).

After 14-weeks of PEERS training, subjects will return for a post-treatment session in which the clinical outcome measures will be completed by parents and fMRI session will be completed by the participants (same procedures as before excluding tDCS acclimation).

Finally, 14 weeks after the post-treatment session, the parent will be sent a reminder via RedCap to complete the clinical outcome measures. In addition, both parent and child will be asked to guess which condition the child was assigned to (active or sham tDCS). Once the final follow-up surveys are completed in RedCap, the final gift card of \$75 is mailed to the family.

Information about which condition a subject was assigned to is not typically provided, but if a subject asks, we can tell them after all study procedures are completed and the blind is lifted. Study personnel will also be asked to guess the condition before the study blind is lifted.

Source records: the data collected from subjects include: parental and subject responses on clinical tests and questionnaires, anatomical and functional MRI scans, reaction time and accuracy responses on the fMRI task.

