This project involves both a medical device intervention (tDCS) and a behavioral intervention (PEERS training). fMRI scanning, while not an intervention, will be conducted prior to and following 14-weeks of weekly tDCS sessions.

For tDCS, safety of the participants will be monitored during and immediately after delivery of tDCS to the scalp. During tDCS stimulation, subjects have the option of wearing a ski cap which may reduce discomfort. They will be introduced to the ski cap during the tDCS acclimation session on the initial visit. Some subjects may opt not to wear the ski cap, but it will not affect tDCS delivery. At the end of the sessions that involved tDCS delivery, subjects will be asked if they felt or feel any sensations on the scalp where the electrode was and responses are recorded by the experimenter. In [name] experience and other reports in the literature, any sensations of pain, tingling, itching, stinging or irritation follow the onset of stimulation for about 30-60 seconds and do not persist longer than that. If subjects report feelings of sensation or pain that are unmanageable, a local analgesic cream (benzocaine) can be used or the level of current can be reduced to help them complete the session. [name] will be present during all experimental sessions when tDCS is delivered and will be able to monitor for any adverse medical effects.

Adverse effects will be defined by painful sensations that are unmanageable and cannot be alleviated using the procedures outlined above or by persistent reports of high levels of pain by a participant. Although we do not expect this to occur, such events will be reported to the IRB.

For PEERS training, which is a behavioral intervention, the risks are minimal, but include potential discomfort in interacting with other individuals. Should this intervention prove to be too distressful for an individual, the individual will have the option to discontinue the study. Distress would be indicated by persistent withdrawal from or refusal to engage in PEERS activity, persistent protesting, crying or agitation during PEERS sessions. [name] and the research assistant will make the decision as to whether an individual is experiencing distress. When these behaviors lead to removal from the study, these will be reported as adverse events to the IRB.

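### Past-week symptoms are asked only after stimulation has begun, so a stable pre-existing complaint can count against the individual 25% tolerability rule

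*Combined protocol and SAP*

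**What the plan says.** Section 10.0 sets the timing: "After the second and last PEERS sessions, the experimenters will administer a brief questionnaire with the subject". Besides local sensations during the session, the questionnaire asks "whether they have had headaches, neck pain, sleepiness, moodiness in the past week". As described, these items record whether a symptom occurred, not whether it changed or what caused it. The text continues "Any of these effects will be recorded" and then gives the decision rule: "We will conclude that tDCS can be tolerated if these effects are experienced less than 25% of the time for a given individual". The number of participants who tolerated the procedures is also to be reported.

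The initial visit in Section 10.0 contains consent, medical and MRI screening, ADOS-2, K-BIT2, parent-completed clinical measures, mock scanner, fMRI and tDCS acclimation. The acclimation ends with current raised over 5 minutes. The nearest thing to a symptom baseline is that "the medical history information obtained during the initial telephone interview will be reconfirmed".

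Two other places bear on the point. Section 4.0 defines the primary safety endpoint as "self-reported adverse effects of tDCS collected after each treatment session", a different frequency from Section 10.0 but also only after stimulation. In Section 13.0, at the end of tDCS sessions, "subjects will be asked if they felt or feel any sensations on the scalp where the electrode was"; the four past-week symptoms are not part of that question. The Aim 1 analysis in Section 12.0 is descriptive frequencies, with no contrast between arms and no change from baseline.

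**The concern.** Headache, neck pain, sleepiness and moodiness can occur in adolescents without any stimulation. The items look back over a week in which stimulation takes 30 minutes. With no value from before the first current, a participant who was always sleepy or moody cannot be told apart from one in whom this began with tDCS. Both answer yes, and both answers appear to enter the individual rule.

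Safety and feasibility is Aim 1. What is at stake is the count of participants who tolerated tDCS. A pre-existing symptom can only move that count down, in the active and the sham arm alike. Once a participant has had the acclimation current, the missing baseline cannot be recovered.

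**Working it through.** **Inputs from the documents.** 17 adolescents enrolled, about 40% drop-out, 10 completers (Section 6.0); half active, half sham (Section 10.0); 14 weekly sessions; questionnaire twice (Section 10.0) or after each session (Section 4.0); limit of 25% per individual.

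**Input not in the documents.** The background frequency p of at least one of the four symptoms. I assume 5% to 50% and show the range.

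**The plan's own figures.** 17 × (1 − 0.40) = 10.2, so 10 completers reproduces, or about 5 per arm. The 25% limit is a fixed rule with no inputs to reproduce it from.

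**Step 1: what the rule can register.** If the share is taken over questionnaires, two administrations allow only 0%, 50% or 100%. One yes gives 50% and fails. With 14 administrations, 3/14 = 21% passes and 4/14 = 29% fails.

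**Step 2: a persistent symptom.** Someone who always has the symptom answers yes every time (100%) and fails under either schedule. With no tDCS effect, P(fail) = p.

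**Step 3: a symptom that comes and goes independently between two questionnaires.** P(fail) = 1 − (1 − p)². If a positive baseline answer discounts later ones (one yes/no composite item), this becomes (1 − p) × [1 − (1 − p)²].

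| p (assumed) | Persistent: fail, no baseline | Expected of 10 | Persistent: fail, with baseline | Independent: fail, no baseline | Independent: fail, with baseline |
|---|---|---|---|---|---|
| 5% | 5% | 0.5 | 0% | 9.8% | 9.3% |
| 10% | 10% | 1 | 0% | 19.0% | 17.1% |
| 20% | 20% | 2 | 0% | 36.0% | 28.8% |
| 30% | 30% | 3 | 0% | 51.0% | 35.7% |
| 50% | 50% | 5 | 0% | 75.0% | 37.5% |

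The persistent columns measure the defect described here, and a baseline removes it. The independent columns mostly reflect symptoms that arise by chance after baseline, which a baseline removes only in part.

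**Step 4: what the sham arm can supply.** With 5 sham completers of whom 1 reports a symptom, the exact 95% interval for the background rate runs from 1 − 0.975^(1/5) = 0.5% up to about 72%, the u that solves (1 − u)⁵ + 5u(1 − u)⁴ = 0.025.

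**The case against.** The strongest reply is that the trial has a blinded, randomised sham arm and nothing limits the questionnaire to one arm. Background symptoms are expected equally in both, so an excess under active stimulation would show in frequencies by arm. This stands at group level. A reader might infer that the missing baseline hides any true worsening in the active arm; the documents do not support that. What remains is that a group rate cannot correct an individual verdict, that about 5 sham completers estimate it very loosely, and that Section 12.0 does not say the Aim 1 frequencies will be shown by arm. Nor is sham entirely free of current: all participants get a brief initial dose, and no sham exception is stated for the acclimation.

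Second, a reader might infer that Aim 1 is decided on these four items. It is not. Section 10.0 also monitors discomfort during delivery, attempts to take off the leads and wishes to stop because of tDCS, and Section 13.0 defines adverse effects separately, by pain.

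Third, that every yes enters the individual verdict is an inference. The rule's reference to effects could mean in-session reports, questionnaire answers or both, its denominator is not stated, and the questionnaire itself is not in the documents. This stands, and it is why the size is conditional. The direction is not.

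Fourth, because sessions are weekly, a one-week recall spans the interval between sessions and can catch delayed effects. That is a fair reason to keep the window, and the point here does not depend on changing it.

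**Conclusion.** The point holds in a limited form. As written, a stable pre-existing symptom can be counted as intolerance of tDCS in an individual, active or sham, and so lower the reported number who tolerated the procedures. The error runs in the cautious direction, in a descriptive pilot.

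The size is about p of participants: 0.5 to 5 of 10 completers for p from 5% to 50%. It rests on three assumptions: the background rate, a symptom that persists within the person, and a verdict taken over questionnaires. It is tempting to quote the larger figures from the independent-weeks model, such as 36% to 75% failing at p of 20% to 50%. The documents give no rate to support them, that model is not the persistent-symptom mechanism, and a baseline would cut them only to 28.8% and 37.5%. Much of their size comes from having only two questionnaires and no defined denominator, which is a separate gap.

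**What to change.** In Section 10.0:

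- Give the same past-week items, with a simple severity grade, at the initial visit before the acclimation current, to the same respondents who answer later.
- Count towards the 25% rule only past-week symptoms that are new or worse than that baseline.
- State the denominator of the rule (questionnaires, sessions or in-session reports).

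In Section 12.0, tabulate baseline and on-treatment frequencies side by side for active and sham. This is needed as well as the baseline, because a baseline does not remove symptoms that newly arise by chance; only the comparison with sham indicates how common those are.

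Sections 4.0 and 10.0 must be reconciled on whether adverse effects are collected after every session or after the second and last only.

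Cost: a few more minutes at an initial visit of about 3 hours, a grade added to items that are now described as yes/no, a short clause in the rule and one table. Nothing in the stimulation or its management changes.

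### Section 4.0 promises adverse-effect reports after every session, Section 10.0 gives the questionnaire after only 2 of 14, and the 25% tolerability rule states no denominator or data source

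*Combined protocol and SAP*

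**What the plan says.** Section 4.0: "The primary safety endpoint will be self-reported adverse effects of tDCS collected after each treatment session".

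Section 10.0: "A brief questionnaire about adverse effects will be completed with participants and their parents immediately following the second and last treatment sessions". The same paragraph repeats that timing. The form asks about uncomfortable itching, tingling or burning in the session just ended, and "whether they have had headaches, neck pain, sleepiness, moodiness in the past week". While current is being delivered, staff also judge tolerance by "noting the frequency with which a subject reported irritation, discomfort, burning or pain", by attempts to pull off the leads, and by any wish to stop because of tDCS. The rule follows directly after the description of the form: "We will conclude that tDCS can be tolerated if these effects are experienced less than 25% of the time for a given individual". The plan then promises to report how many subjects tolerated the procedures.

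Section 13.0 adds a third record. At the end of sessions with tDCS, "subjects will be asked if they felt or feel any sensations on the scalp where the electrode was and responses are recorded by the experimenter". It also uses a narrower definition of adverse effect than the form does: unmanageable pain that the listed measures do not relieve, "or by persistent reports of high levels of pain by a participant".

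Section 12.0 limits the Aim 1 analysis to descriptive statistics by type of discomfort or pain and does not mention the 25% rule. Section 1.0 predicts that tDCS will be tolerable for most participants.

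**The concern.** Two things do not fit together.

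First, following Section 10.0 does not deliver the endpoint in Section 4.0. The in-session notes and the end-of-session question deal with what is felt during stimulation or at the electrode site. Headache, neck pain, sleepiness and moodiness are asked about on the two forms only, with one-week recall. Section 15.0 itself lists headache as a reported effect of tDCS. Answers for weeks that were never asked about cannot be recovered later.

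Second, a cut-off of 25% needs a denominator, and none is given. The wording could refer to forms, to single answers on the forms, or to sessions. The text leans towards the two forms, because the form's list of effects comes immediately before the rule, but with two occasions a 25% threshold has nothing to separate. The analyst would have to choose a reading after the data are in, and that choice decides who is counted as tolerating tDCS.

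**Working it through.** **Inputs.** Fourteen weekly sessions with tDCS at each (Section 10.0); two forms, after sessions 2 and 14, with one-week recall for four effects (Section 10.0); 17 adolescents randomised and 10 expected to complete (Sections 6.0 and 10.0). The 25% is a chosen cut-off, so there is no derived figure to reproduce.

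**1. Coverage of the four past-week effects.** The form after session 2 looks back over the week after session 1. The form after session 14 looks back over the week after session 13. Covered: 2/14 = 14.3% of post-session weeks. With a form at every session, those at sessions 2 to 14 would cover 13/14; the week after session 14 is not asked about either way.

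**2. What the rule allows under each reading.**

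| Reading | Denominator | Most positives below 25% |
|---|---|---|
| Any effect, per form | 2 | 0 (1/2 = 50%) |
| Single answers on the forms | 7 items × 2 = 14 | 3 (3/14 = 21.4%; 4/14 = 28.6%) |
| Any effect, per session | 14 | 3 (same fractions) |

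**3. The same person under two readings.** A local effect at session 2 only gives 1/2 = 50% on the forms (not tolerated) and 1/14 = 7.1% per session (tolerated). In the other direction, effects at all 12 sessions without a form give 0/2 = 0% on the forms (tolerated) and 12/14 = 85.7% per session (not tolerated). Neither result needs an assumed rate.

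**4. Drop-outs.** 17 − 10 = 7, and 7/17 = 41.2%. Anyone who stops without notice after session 2 leaves one form, so only 0% or 100% is possible for the past-week effects. The timing of drop-out is not given, so 7 is an upper limit.

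**5. Weight of one person in the promised count.** 1/17 = 5.9% of those randomised; 1/10 = 10% of completers.

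**6. Illustration only.** Let p be the mean chance of an effect at a session and r the within-person correlation. The documents give neither; the values below are assumptions. Not tolerating on two forms: 1 − [(1 − p)² + r·p(1 − p)]; for p = 0.10 and r = 0.1 this is 1 − (0.81 + 0.009) = 18.1%. Not tolerating on 14 sessions: the chance of 4 or more affected sessions under a beta-binomial model. The two forms are 2 of the 14 sessions.

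| r | p | Two forms | 14 sessions | Classed differently |
|---|---|---|---|---|
| 0 | 0.10 | 19.0% | 4.4% | 18.7% |
| 0 | 0.20 | 36.0% | 30.2% | 32.1% |
| 0 | 0.30 | 51.0% | 64.5% | 36.3% |
| 0.1 | 0.10 | 18.1% | 11.7% | 15.7% |
| 0.1 | 0.20 | 34.4% | 32.8% | 25.6% |
| 0.1 | 0.30 | 48.9% | 56.0% | 29.2% |
| 0.3 | 0.10 | 16.3% | 14.9% | 10.3% |
| 0.3 | 0.20 | 31.2% | 31.4% | 16.7% |
| 0.3 | 0.30 | 44.7% | 47.8% | 19.8% |

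At correlations of 0.1 to 0.3 the group proportion differs by 0.2 to 7.1 percentage points. With independent sessions it differs by up to 14.6 (19.0 − 4.4). As a comparison of two readings of the present text, the table applies to local effects only, since the plan collects nothing at 14 sessions for the other four.

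**The case against.** The strongest reply is that Section 4.0 names no questionnaire and no list of effects, and that self-report after each session does exist: Section 13.0 has subjects asked about scalp sensations and the answers recorded. That stands. A reader might infer that adverse effects go unrecorded at 12 of 14 sessions; the documents do not support this. The shortfall is confined to four effects.

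Several other tempting readings also fail. The rule is not silent on whom it judges, because it is applied to each individual. The respondent is not truly open either: Section 10.0 mentions parents in one sentence and the subject alone in another, but Section 4.0 says self-reported. One might weigh each person at 20 percentage points by counting only about 5 active completers, but Section 10.0 speaks of subjects without limiting the count by arm, and Aim 1 covers active and sham. Nor is the rule the only sign of tolerance, since lead removal and wish to stop are also noted.

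Finally, one may say that the group count hardly moves and that nothing is decided on it. At the correlated values above the first part is mostly right, though it rests on assumed rates. The second part is right: the planned Aim 1 analysis does not use the rule. This limits the weight of the point. It does not remove the conflict between Sections 4.0 and 10.0 or supply the missing denominator.

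**Conclusion.** The point holds and should be fixed, as a weakness of data collection and reporting. Two results come from the documents alone: four listed effects are asked about for 2 of 14 post-session weeks although the primary safety endpoint is promised for every session; and the 25% rule, on its nearest reading with any-effect scoring, reduces to no effect on either form, whereas per session it allows 3 of 14. Those readings can put the same person on opposite sides.

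The result affected is the count of subjects who tolerated tDCS, where each person is about 6 to 10 percentage points. How far that count, or individual classification, would shift depends on assumed rates and correlations, so those figures illustrate and do not estimate. A reader might infer a threat to participant safety; the documents do not support that, because effects during and just after stimulation are monitored at each session and no stopping decision rests on the rule.

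**What to change.** Reconcile Sections 4.0, 10.0 and 13.0.

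- **Collection.** Give the same brief questionnaire, with one list of effects, after every tDCS session, as Section 4.0 already states. Say which definition of adverse effect the endpoint uses, since Section 13.0 has a narrower one.
- **Rule.** Define it as assessed sessions with an effect divided by sessions assessed, below 25%, from the adolescent's self-report. Show any parent report separately.
- **Attribution.** Compute it separately for local effects (attributed to that session, at most 14) and past-week effects (attributed to the preceding session, at most 13), so that one session cannot count twice. The session 1 past-week answers serve as baseline; record the date of the acclimation visit, because current is delivered there. State in advance whether a single headline count requires both results to be below 25%.
- **Reporting.** Include drop-outs with the sessions they have and give the number assessed per person. The rule allows 0 affected sessions of 1–4, 1 of 5–8, 2 of 9–12 and 3 of 13–14, so it is coarse for short follow-up. Show frequencies by effect type and arm, beside the number who stopped because of tDCS.

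If only two forms are kept, correct Section 4.0 to say so, apply the 25% rule only to the local effects recorded at each session, and report the four past-week effects descriptively.

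Cost: up to 12 more short forms per person at sessions already attended, 12 × 10 = 120 for completers and at most 12 × 17 = 204 for all randomised. There are no extra visits. The two-form alternative changes wording only, but leaves the four effects unasked in 12 of 14 post-session weeks.

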- **Aim 1.** Establish the safety and feasibility of administering active and sham tDCS with PEERS training in adolescents with ASD. We predict that tDCS administered with 1.5mA current will be safe for participants and tolerable for the majority of participants.
- **Aim 2.** Examine the impact of tDCS in improving social skills and attention to faces. We predict that active tDCS in conjunction with PEERS training will improve social function and attention to faces to a greater degree than sham tDCS plus PEERS training.
- **Aim 3.** Examine the impact of tDCS on neural correlates of social function and attention to faces using functional magnetic resonance imaging (fMRI). We predict that activity in regions that underlie social behavior (e.g., medial prefrontal cortex, temporoparietal junction, fusiform gyrus, amygdala) will increase more in response to social stimuli following active tDCS with PEERS training compared to sham tDCS with PEERS training.

Impact. The present study will address the need to find approaches to enhance social learning in ASD. Social communication difficulties may become especially apparent during adolescence, a time period marked by greater emphasis on social relationships and peer influence. Therefore, the present strategy is to examine the efficacy of a minimally invasive neuromodulatory technique in adolescents in combination with an evidence-based behavioral intervention, PEERS, to enhance social information processing and social interaction, with fMRI markers of neural plasticity before and after intervention.

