14.0 Withdrawal of Subjects (if applicable)

Subjects can withdraw from the study voluntarily. Although financial incentives will be provided for continued participation, subjects are not forced or otherwise coerced to participate.

The investigators may withdraw an individual from the study for the following reasons: (a) participant does not understand or follow instructions, (b) participant is not cooperative or is disruptive during PEERS/ tDCS delivery or fMRI scanning sessions, (c) the safety of the individual is at risk due to tDCS

delivery, as described above (persistent or intense experience of pain), (d) the subject exhibits severe psychological distress or anxiety during tDCS delivery, PEERS activities or fMRI scanning. If any of these reasons leads to withdrawal from the study, Drs. [name] / [name] would discuss the reason(s) with the child and parent as soon as possible following the incident. This could be immediate if only the volunteer would be affected (e.g., during fMRI scanning), but if there are disruptions or a failure to follow instructions during a PEERS session (which takes place in a group format), [name] will discuss the issue with the parents following the session.

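### The 25% tolerability rule counts only how often effects occur, so an adolescent who stops because of tDCS can, though will not always, be classed as having tolerated it

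*Combined protocol and SAP*

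**What the plan says.** All references are to the combined protocol and SAP.

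- **Aim (1.0).** Stimulation at the study current is predicted to be safe and "tolerable for the majority of participants".
- **What is observed (10.0).** During delivery, staff note how often irritation, discomfort, burning or pain is reported, "whether a subject attempted to remove the tDCS leads", and "whether a subject wished to discontinue the procedures due to the tDCS (rather than the PEERS training"). A questionnaire then asks "whether they felt uncomfortable itching, tingling, burning during the session or whether they have had headaches, neck pain, sleepiness, moodiness in the past week".
- **The rule (10.0).** Directly after that symptom list comes the only decision rule: "We will conclude that tDCS can be tolerated if these effects are experienced less than 25% of the time for a given individual". The number of subjects who tolerated the procedures is also to be reported, with no separate definition.
- **Timing.** Section 10.0 gives the questionnaire "immediately following the second and last treatment sessions". Section 4.0 defines the primary safety endpoint as "self-reported adverse effects of tDCS collected after each treatment session". Section 13.0 also describes asking about scalp sensations at the end of sessions in which tDCS was delivered.
- **Analysis (12.0, Aim 1).** Descriptive only: how often each type of discomfort or pain is reported.
- **Withdrawal (14.0).** Investigators may withdraw a participant where "the safety of the individual is at risk due to tDCS" delivery, explained as persistent or intense pain. Nothing links this to the tolerability rule.

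**The concern.** Stopping because of the stimulation is the most direct evidence that it was not tolerated. The plan observes it but gives it no weight of its own. Under the rule a stop matters only through the effects reported around it, as one or a few occasions in a rate. Even if the effects meant by the rule are read to include lead removal and the wish to discontinue, each is still one event in a frequency. The classification can then turn on when a participant stops, and on which denominator is chosen, rather than on why they stopped.

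Tolerability is half of the Aim 1 prediction, and the count of subjects who tolerated tDCS is the figure a reader will take from it. If participants who left because of tDCS are included in that count, it is too favourable.

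**Working it through.** **Inputs.** 17 adolescents randomised, about 40% drop-out, 10 with complete data (6.0, 10.0); 14 weekly sessions (10.0); threshold below 25% per individual (10.0); questionnaires after the second and last sessions (10.0). The plan does not define the unit or the denominator of the 25%. I assume that an occasion counts as affected if any listed effect is reported on it.

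**Step 1. The plan's own figure.** 17 × (1 − 0.40) = 10.2, i.e. 10 completers, which reproduces Section 6.0. Expected drop-outs: 17 − 10 = 7, or 7/17 = 41%. The 25% threshold is given without a derivation, so there is nothing to reproduce for it.

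**Step 2. Classify an adolescent who stops because of tDCS at session k (k = 1 to 13).** Session 14 is completion, so there are 13 early-stopping points.

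| Denominator | Calculation | Result |
|---|---|---|
| Sessions received, only the stopping session affected | 1/k < 0.25 | Fails at k = 1 to 4 (1/4 = 25%); passes at k = 5 to 13 (1/5 = 20% down to 1/13 = 7.7%), i.e. 9 of 13 points |
| 14 planned sessions | e/14 < 0.25, e = affected sessions | Up to e = 3 passes (3/14 = 21.4%); e = 4 fails (4/14 = 28.6%) |
| Questionnaires completed | 0/1, or 0/2, 1/2, 2/2 | Passes only with no effects reported; any reported effect gives at least 50% and fails |

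With 14 planned sessions, a participant affected at every session attended who stops at session 1, 2 or 3 scores 7.1%, 14.3% or 21.4%, and passes each time.

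With questionnaires, a participant who stops later with a clean session-2 form and no further form scores 0/1 = 0% and passes. One who stops before session 2 has no rate. One who completes a form at the final attended session and reports an effect there fails.

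**Step 3. Effect on the reported count.** Let s be the number who stop because of tDCS. The documents do not give s; 0 to 7 is an assumed range. Assume that all s pass the rule as written and that everyone else tolerates tDCS. The rule then reports 17/17 = 100%. Counting stops as failures gives (17 − s)/17:

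| s | Tolerated if stops count as failures |
|---|---|
| 0 | 17/17 = 100% |
| 2 | 15/17 = 88% |
| 4 | 13/17 = 76% |
| 7 | 10/17 = 59% |

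Even at s = 7 the majority prediction survives if all 10 completers tolerate tDCS. It would fail if only 8 of them did: 8/17 = 47%, against (8 + 7)/17 = 88% under the rule as written.

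**The case against.** **The count may be separate from the rule.** The sentence on how many subjects tolerated the procedures might mean those who did not discontinue, reported alongside the symptom rule. That reading is possible but is not stated, and it leaves the 25% conclusion itself unchanged.

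**The rule is not always lenient.** A reader might infer that anyone who quits is scored as tolerating. The documents do not support that. With sessions received as the denominator, stopping early also removes uneventful sessions, and a stop at sessions 1 to 4 with an effect fails. On the two-questionnaire reading any reported effect fails, which may be stricter than intended. Persistent pain, one of the Section 14.0 grounds, would usually produce several affected sessions and could fail without any change. This stands, and it limits the point to a possibility of misclassification.

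**The drop-outs need not be due to tDCS.** A reader might take the expected 7 as intolerance, or build an example in which half of the active arm leaves because of stimulation. No section attributes drop-out to tDCS. Section 5.0 discontinues participants whose treatment changes, and Section 14.0 lists instructions, cooperation, PEERS and MRI reasons. The leaver counts above are therefore hypothetical. This also stands.

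**The stakes are limited.** Aim 1 is descriptive, the wish to discontinue is noted, unmanageable or persistent pain is reported to the IRB (13.0), and 17 cases could be reclassified at reporting. All true, but reclassifying after the data are seen is a post hoc choice of definition, which one sentence now would avoid.

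**Conclusion.** The point holds as a possibility, under each of the three denominators: the stated rule can class a participant who stopped because of tDCS as having tolerated it, and no other section prevents this. It does not hold for every stopper, and the direction and size of any error depend on a denominator that the plan leaves open.

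The effect on the tolerated proportion ranges from none to a fall from 100% to 59% (10/17). The lower figure requires all 7 expected drop-outs to be due to tDCS, all of them to pass the current rule, and everyone else to tolerate it. The documents support none of these as a forecast, so this is a bound and not an estimate of bias. Nor do they support a claim that the error is larger in the active arm. No hypothesis test is affected. The change is still worth making, because the rule addresses the Aim 1 question directly and the defect is in the classification itself.

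**What to change.** In the analysis rule of Section 10.0:

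1. State that any participant who stops tDCS, declines further tDCS, or is withdrawn under Section 14.0, because of tDCS, is counted as not tolerating it, whatever the frequency of effects.
2. Define the unit and denominator behind the 25%, and reconcile Sections 4.0 and 10.0 on when effects are collected.
3. Record a reason for every discontinuation. The present text notes a wish to discontinue during delivery, but not why a participant simply fails to return.
4. Among all who started randomised tDCS sessions, report by arm the number tolerating and the number stopping because of tDCS. Report stops at acclimation separately and not by arm, because Section 10.0 describes current being raised at acclimation without distinguishing active from sham.

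These definitions should be settled before the blind is lifted. They concern classification and reporting only and change no dose, schedule or withdrawal criterion. The cost is a few sentences of wording and one extra recorded item per discontinuation. The downside is a possibly less favourable tolerability figure.
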